6.2 Exclusion Criteria

1) Medical Conditions

a) Women who are pregnant or breastfeeding.

2) Prior/Concomitant Therapy

a) Cytotoxic agents, unless at least 4 weeks have elapsed from last dose of prior anti-cancer therapy and initiation of study therapy.

Protocol Amendment No.: 07

b) Non-cytotoxic agents, unless at least 4 weeks or 5 half-lives (whichever is shorter) have elapsed from the last dose of prior anti-cancer therapy and the initiation of study therapy.

- c) Prior immune therapy treatments, unless at least 4 weeks or 5 half-lives (whichever is shorter) have elapsed from the last dose of immune therapy and initiation of study therapy.
- d) Prior participation in an anti-TIM-3 clinical study.
- e) Treatment with botanical preparations (eg, herbal supplements or traditional Chinese medicines) intended for general health support or to treat the disease under study within 2 weeks prior to randomization/treatment. Refer to Section 7.7.1 for prohibited therapies.
- f) Prior radiation therapy within 2 weeks prior to first study treatment. Participants must have recovered (ie, Grade ≤1 or at baseline) from radiation-related toxicities prior to first study treatment.

3) Medical History and Concurrent Diseases

- a) Participants with concomitant second malignancies (except adequately treated nonmelanomatous skin cancers or in situ bladder, breast, or cervical cancers) are excluded unless a complete remission was achieved at least 2 years prior to study entry, and no additional therapy is required or anticipated to be required during the study period.
 - i) In addition, in Part C, participants with concurrent malignancies that do not require treatment and are clinically stable and anticipated to be followed in an active surveillance manner for the next 12 months are eligible. Treatment should not be required at timing of consent and not be expected to be needed not only for the concurrent malignancy, but also for complications caused by it. The Investigator should inform the participant that the study treatment is not intended and not expected to be considered as treatment for the concurrent malignancy.
- b) Participants with other active malignancy requiring concurrent intervention.
- c) Prior organ or tissue allograft.
- d) Toxicity (except for alopecia) related to prior anti-cancer therapy and/or surgery, unless the toxicity is either resolved, returned to baseline or Grade 1, or deemed irreversible.
 - i) Any active neuropathy > Grade 2 (National Cancer Institute [NCI] common Terminology Criteria for Adverse Events [CTCAE] v4.03)
- e) Participants with the following:
 - i) Active, known, or suspected autoimmune disease.
 - (1) Participants with well-controlled asthma and/or mild allergic rhinitis (seasonal allergies) are eligible.
 - (2) Participants with the following disease conditions are also eligible:
 - (a) Vitiligo.
 - (b) Type 1 diabetes mellitus on stable conditions under insulin treatment.
 - (c) Residual hypothyroidism due to autoimmune condition only requiring hormone replacement.
 - (d) Euthyroid participants with a history of Grave's disease (participants with suspected autoimmune thyroid disorders must be negative for thyroglobulin and

- thyroid peroxidase antibodies and thyroid stimulating Ig prior to the first dose of study drug).
- (e) Psoriasis not requiring systemic treatment, or conditions not expected to recur in the absence of an external trigger are permitted to enroll.
- ii) History of life-threatening toxicity related to prior immune therapy (eg, anti-CTLA-4 or anti-PD-(L)1 treatment or any other antibody or drug specifically targeting T cell co-stimulation or immune checkpoint pathways) except those that are unlikely to re-occur with standard countermeasures (eg, hormone replacement after adrenal crisis).
- iii) Participants with a condition requiring systemic treatment with either corticosteroids (> 10 mg daily prednisone equivalent) within 14 days or other immunosuppressive medications within 30 days of treatment assignment. Inhaled or topical steroids, and adrenal replacement steroid doses > 10 mg daily prednisone equivalent, are permitted in the absence of active autoimmune disease.
- iv) Uncontrolled or significant cardiovascular disease including, but not limited, to any of the following:
 - (1) Myocardial infarction or stroke/transient ischemic attack within the past 6 months
 - (2) Uncontrolled angina within the past 3 months
 - (3) Any history of clinically significant arrhythmias (such as ventricular tachycardia, ventricular fibrillation, or torsades de pointes)
 - (4) History of other clinically significant heart disease (eg, cardiomyopathy, congestive heart failure with New York Heart Association functional classification III to IV [Appendix 7])
 - (5) Cardiovascular disease-related requirement for daily supplemental oxygen therapy
 - (6) QT interval corrected for heart rate using Fridericia's formula (QTcF) prolongation > 480 msec, except for right bundle branch block
 - (7) History of myocarditis, regardless of etiology
- v) History of or with active interstitial lung disease
- vi) History of chronic hepatitis as evidenced by the following:
 - (1) Positive test for hepatitis B surface antigen
 - (2) Positive test for qualitative hepatitis C viral load by polymerase chain reaction (PCR)
 - (3) Participants with positive hepatitis C antibody and negative quantitative hepatitis C by PCR are eligible. History of resolved hepatitis A virus infection is not an exclusion criterion.
 - (4) Additional testing or substitute testing per institutional guidelines to rule out infection is permitted.
- vii) Evidence of active infection that requires systemic antibacterial, antiviral, or antifungal therapy ≤ 7 days prior to the first dose of study drug (except for viral infections that are presumed to be associated with the underlying tumor type required for study entry).
- viii) Human immunodeficiency virus (HIV) or known acquired immunodeficiency syndrome:

CA031002 Anti-TIM-3 mAb

(1) For Parts A, A1, and B, known history of testing positive for HIV or known acquired immunodeficiency syndrome constitutes an exclusion criterion.

Note: Testing for HIV must be performed at sites where mandated by local requirements.

- (2) For Part C, HIV infection does not constitute an exclusion criterion if the following conditions are satisfied:
 - (a) Subject is in use of an antiretroviral therapy regimen for > 4 weeks.
 - (b) HIV viral load is undetectable or below the lower limit of detection as per local testing standards.
 - (c) CD4+ T-cell counts >= 350 cells/mL, up to 4 weeks prior to enrollment.
 - (d) Subject has no history of AIDS-defining opportunistic infections.
- ix) Any major surgery within 4 weeks of the first dose of study drug. Participants must have recovered from the effects of major surgery or significant traumatic injury at least 14 days before the first dose of study drug.
- x) Receipt of non-oncology vaccines containing live virus for prevention of infectious diseases within 4 weeks prior to first dose of study drug.
 - (1) The use of inactivated seasonal influenza vaccines (eg, Fluzone®) will be permitted on study without restriction.
- xi) Receipt of packed red blood cells or platelet transfusion within 2 weeks of the first dose of study drug unless agreed by the Medical Monitor.
- xii) Any known or underlying medical, psychiatric condition, and/or social reason that, in the opinion of the Investigator or Sponsor, could make the administration of study drug hazardous to the participants or could adversely affect the ability of the participant to comply with or tolerate the study.
- xiii) Previous SARS-CoV-2 infection within 10 days for mild or asymptomatic infections or 20 days for severe/critical illness prior to Cycle 1 Day 1.
 - (1) Acute symptoms must have resolved and based on investigator assessment in consultation with the Medical Monitor, there are no sequelae that would place the participant at a higher risk of receiving study treatment.
- xiv) Previous SARS-CoV-2 vaccine within 14 days of Cycle 1 Day 1. For vaccines requiring more than one dose, the full series (eg, both doses of a two-dose series) should be completed prior to Cycle 1 Day 1 when feasible and when a delay in Cycle 1 Day 1 would not put the study participant at risk.
- xv) Symptomatic central nervous system (CNS) metastases. Participants are eligible if CNS metastases are asymptomatic and do not require immediate treatment or have been treated and participants have neurologically returned to baseline (except for residual signs or symptoms related to the CNS treatment). In addition, participants must have been either off corticosteroids, or on a stable or decreasing dose of ≤ 10 mg daily prednisone (or equivalent) for at least 2 weeks prior to treatment assignment. In case of past or suspect CNS metastases, imaging performed

Protocol Amendment No.: 07

assignment must document radiographic stability of CNS lesions and be performed after completion of any CNS-directed therapy.

xvi) Leptomeningeal metastases.

4) Allergies and Adverse Drug Reaction

- a) History of allergy or hypersensitivity to study drug components.
- b) History of severe hypersensitivity reaction to any mAb.

5) Other Exclusion Criteria

- a) Prisoners or participants who are involuntarily incarcerated. (Note: under certain specific circumstances and only in countries where local regulations permit, a participant who has been imprisoned may be permitted to continue as a participant. Strict conditions apply and Bristol-Myers Squibb (BMS) approval is required).
- b) Participants who are compulsorily detained for treatment of either a psychiatric or physical (eg, infectious disease) illness.

Eligibility criteria for this study have been carefully considered to ensure the safety of the study participants and that the results of the study can be used. It is imperative that participants fully meet all eligibility criteria and confirmed prior to Cycle 1 Day 1.

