 - (4) At screening, the Investigator should document on the electronic case report form (eCRF) the progression date and criteria used in determining disease progression from prior anti-PD-(L)1 therapy (eg, RECIST v1.1, irRC, irRECIST, and/or iRECIST).

3) Physical and Laboratory Findings

- a) Adequate hematologic function for participants as defined by the following:
 - i) Neutrophils $\geq 1500/\mu L$ (use of growth factors to achieve this level is not permitted within 2 weeks prior to screening laboratories).
 - ii) Platelets $\geq 80 \times 10^3 / \mu L$ (transfusion to achieve this level is not permitted within 2 weeks prior to screening laboratories).
 - iii) Hemoglobin ≥ 8 g/dL (transfusion to achieve this level is not permitted within 2 weeks prior to screening laboratories).
- b) Adequate hepatic function
 - i) Alanine aminotransferase (ALT) and aspartate aminotransferase (AST) \leq 3 \times upper limit of normal (ULN).
 - ii) Total bilirubin $\leq 1.5 \times \text{ULN}$ (except participants with Gilbert's syndrome who must have normal direct bilirubin).
- c) Clinically stable thyroid function per Investigator assessment.
- d) Serum creatinine $\leq 1.5 \times ULN$ or creatinine clearance (CrCl) ≥ 40 mL/min (measured using the Cockcroft-Gault formula below):

Female CrCl =
$$(140 - age in years) \times weight in kg \times 0.85$$
 $72 \times serum creatinine in mg/dL$

Male CrCl = $(140 - age in years) \times weight in kg \times 1.00$
 $72 \times serum creatinine in mg/dL$

e) Ability to comply with treatment, PK and PD sample collection, and required study follow-up periods.

4) Age and Reproductive Status

- a) Males and females ages 18 years, or age of majority, or older at time of consent.
- b) Women of childbearing potential (WOCBP) must have a negative serum or urine pregnancy test (minimum sensitivity 25 IU/L or equivalent units of human chorionic gonadotropin) within 24 hours prior to the start of study treatment. An extension up to 72 hours prior to the start of study treatment is permissible in situations where results cannot

- be obtained within the standard 24-hour window. Additional requirements for pregnancy testing during and after study intervention are located in Schedule of Activities.
- c) WOCBP must agree to follow instructions for method(s) of contraception (Appendix 4) and as described below and included in the ICF. WOCBP are permitted to use hormonal contraception methods (as described in Appendix 4).

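### The Part C CD4 minimum for participants with HIV is given per mL, not per microlitre, so as written it excludes practically no one

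*Combined protocol and SAP*

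**What the plan says.** Section 6.2, exclusion criterion 3e(viii), treats HIV differently by study part. In Parts A, A1 and B, a known positive HIV history or known AIDS is an exclusion. Part C has an exception: "For Part C, HIV infection does not constitute an exclusion criterion if the following conditions are satisfied". Four conditions follow:

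- (a) more than 4 weeks on antiretroviral treatment;
- (b) a viral load that the local assay cannot detect;
- (c), the condition at issue here: "CD4+ T-cell counts >= 350 cells/mL, up to 4 weeks prior to enrollment";
- (d) no past opportunistic infection of the kind that defines AIDS.

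The other blood cell minimums for entry are in Section 6.1, criterion 3a. The neutrophil criterion is "Neutrophils $\geq 1500/\mu L$ (use of growth factors to achieve this level is not permitted within 2 weeks prior to screening laboratories". The platelet criterion is 80 × 10³ per microlitre. Both use the microlitre. The CD4 minimum appears nowhere else in the document, in either unit.

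**The concern.** The CD4 condition uses a volume unit 1000 times larger than the one used for the protocol's other blood cell minimums. Read literally, its threshold is so low that it no longer selects anyone.

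The stakes are in safety. Condition (c) is the only one of the four that sets a minimum current immune-cell count. The dose-escalation parts exclude people with known HIV, so Part C is where such participants would first receive the combination in this trial. Section 3.3.7 warns that the combination may cause increased or unexpected immune-related events.

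The literal text also carries weight. Section 6.2 closes by requiring every eligibility criterion to be met in full, and Section 9 allows no waivers. A site that enrols a participant with 100 CD4 cells per microlitre meets condition (c) as written. A site that turns the same person away on that ground applies a limit the protocol does not state.

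**Working it through.** The plan gives no derived figure to reproduce. The check is a unit conversion and a pass/fail comparison.

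**Inputs**

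- CD4 minimum: 350 cells per mL (Section 6.2, 3e(viii)(2)(c)).
- Neutrophil minimum: 1500 per microlitre (Section 6.1, 3a(i)).
- Platelet minimum: 80 × 10³ per microlitre (Section 6.1, 3a(ii)).
- 1 mL = 1000 microlitres.

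**Step 1. Thresholds in common units**

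| Item | Per microlitre | Per mL |
|---|---|---|
| CD4, as written | 350 / 1000 = 0.35 | 350 |
| CD4, if per microlitre was meant | 350 | 350 × 1000 = 350,000 |
| Neutrophils | 1500 | 1500 × 1000 = 1,500,000 |
| Platelets | 80,000 | 80,000 × 1000 = 80,000,000 |

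The two readings of the CD4 line differ by 350,000 / 350 = 1000.

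**Step 2. Who passes condition (c)**

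A count of *c* per microlitre passes the text as written if 1000 × *c* ≥ 350. It passes the per-microlitre reading if *c* ≥ 350.

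| CD4 count per microlitre | As written (per mL) | Per microlitre |
|---|---|---|
| 0 | fails | fails |
| 1 | passes (1000 ≥ 350) | fails |
| 10 | passes | fails |
| 50 | passes | fails |
| 200 | passes | fails |
| 349 | passes | fails |
| 350 | passes | passes |

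As written, only a count of essentially zero fails. Every count from 1 to 349 per microlitre changes from pass to fail once the unit is per microlitre.

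**The case against.** **It may be a misread character.** The point turns on one letter, and a micro sign can become an m when a PDF is converted to text. Other symbols in the document are visibly damaged, for example in Sections 5.4.5 and 5.4.7. This cannot be excluded without looking at the page. Against it, the micro sign is intact in Sections 5.5.1 and 6.1, Greek letters survive in ordinary text, and the inequality in the CD4 line is typed as two keyboard characters. That fits an author's slip better than a conversion fault.

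**Other safeguards remain.** This stands. Conditions (a), (b) and (d) are unaffected. Criterion 3e(vii) excludes active infection needing systemic treatment, and 3e(xii) lets the investigator or sponsor exclude anyone for whom study drug could be hazardous. What is lost is the CD4 minimum alone.

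**Sites will see the slip.** A threshold of 0.35 per microlitre is odd enough that many sites may read it as per microlitre or ask, and nothing in the documents shows that anyone would enrol on the literal reading. That lowers the likely harm. It does not make the text right: the rule then depends on each site's guess, and a monitor could not call a literal application of (c) a deviation.

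**It is a small, non-statistical error.** It reaches only participants with HIV in Part C and touches no endpoint, estimate, dose decision or sample size. That limits its importance. It is still the decision threshold of a safety criterion, not background text.

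**Conclusion.** The concern holds. As written, the CD4 minimum is 0.35 cells per microlitre, 1000 times lower than the same number per microlitre, and condition (c) excludes practically no one.

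The conclusion rests on two points. First, the text read here matches the protocol page; the PDF can settle this at once. Second, per microlitre is taken as the intended unit. That is inferred from the neutrophil and platelet criteria and from the fact that 0.35 per microlitre cannot work as a threshold. The documents do not state it.

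The effect is confined to eligibility and safety in Part C, where three of the four HIV conditions still apply. It should be corrected, but it does not bear on the trial's analyses.

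**What to change.** In Section 6.2, criterion 3e(viii)(2)(c), change the unit from cells per mL to cells per microlitre, after the sponsor confirms that 350 per microlitre is the intended minimum. Check that the eligibility form and any site eligibility checklist carry the same unit.

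The cost is one unit in one line, which can go into the next amendment. Until then, a written clarification to Part C sites would keep them from applying different rules. If any participant with HIV has already entered Part C, the recorded CD4 count should be checked against the confirmed threshold. No sample size, endpoint or analysis needs to change.

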6.3 Lifestyle Restrictions

Not applicable. No restrictions are required.

6.4 Screen Failures

Screen failures are defined as participants who consent to participate in the clinical study but are not subsequently treated in the study/included in the analysis population. A minimal set of screen failure information is required to ensure transparent reporting of screen failure participants, to meet the Consolidated Standards of Reporting Trials publishing requirements, as applicable, and to respond to queries from regulatory authorities. Minimal information includes date of consent, demography, screen failure details, eligibility criteria, and any serious AEs. If re-enrolled, the participant must be reconsented.

6.4.1 Retesting During Screening or Lead-In Period

This study permits the re-enrollment of a participant that has discontinued the study as a pretreatment failure (eg, participant has not been treated). If re-enrolled, the participant must be re-consented.

Retesting of laboratory parameters and/or other assessments within any single Screening or Leadin period will be permitted (in addition to any parameters that require a confirmatory value).

The most current result prior to Treatment is the value by which study inclusion will be assessed, as it represents the participant's most current clinical state.

Laboratory parameters and/or assessments that are included in may be repeated in an effort to find all possible well-qualified participants. Consultation with the Medical Monitor may be needed to identify whether repeat testing of any particular parameter is clinically relevant.

Protocol Amendment No.: 07

Testing for asymptomatic SARS-CoV-2 infection by reverse transcription polymerase chain reaction (RT-PCR) or viral antigen is not required. However, some participants may develop suspected or confirmed symptomatic SARS-CoV-2 infection or be discovered to have asymptomatic SARS-CoV-2 infection during the screening period. In such cases, participants may be considered eligible for the study after meeting all inclusion/exclusion criteria related to active infection, and after meeting the following criteria:

- At least 10 days (20 days for severe/critical illness) have passed since symptoms first appeared or positive RT-PCR or viral antigen test result
- At least 24 hours have passed since last fever without the use of fever-reducing medications
- Acute symptoms (eg, cough, shortness of breath) have resolved
- In the opinion of the investigator, there are no SARS-CoV-2 infection sequelae that may place the participant at a higher risk of receiving investigational treatment

In the instance of a SARS-CoV-2 infection during screening, the screening period may be extended beyond the protocol-specified timeframe with Medical Monitor approval.

• Any screening tests already performed which could potentially be affected by the SARS-CoV-2 infection or its complications on an individual basis and agreed upon with the Medical Monitor (eg, safety labs, oxygen saturation, chest CT scan) should be repeated.

7 TREATMENT

Study treatment is defined as any investigational treatment(s), marketed product(s), placebo, or medical device intended to be administered to a study participant according to the study randomization or treatment allocation.

Study treatment includes both Investigational [Medicinal] Product (IP/IMP) and Non-investigational [Medicinal] Product (Non-IP/Non-IMP) and can consist of the following:

- BMS-986258
- Nivolumab
- ENHANZE[®] Drug Product (rHuPH20)

An IP, also known as IMP in some regions, is defined as a pharmaceutical form of an active substance or placebo being tested or used as a reference in a clinical study, including products already with a marketing authorization but used or assembled (formulated or packaged) differently than the authorized form, or used for an unauthorized indication, or when used to gain further information about the authorized form.

Drugs used in this open-label study qualify as IPs. Their description and storage information are described in Table 7-1. Please refer to the Pharmacy Manual for additional information.

Protocol Amendment No.: 07

Table 7-1: Study Treatments for CA031002

Product Description/Class and Dosage Form	Potency	IP/Non-IMP	Blinded or Open Label	Packaging / Appearance	Storage Conditions (per label)
BMS-986258		IP	Open Label	Kit	Refer to Product label
BMS-986258		IP	Open Label	Kit	Refer to Product label
Nivolumab	100 mg/vial (10 mg/mL)	IP	Open Label	Kit	Refer to Product label
ENHANZE [®] Drug Product (rHuPH20) ^a	1 mg/mL	IP	Open Label	Vial and various packaging configurations	Refer to the label on container or package insert

Abbreviations: IP, Investigational Product; IMP, Investigational Medicinal Product; rHuPH20, recombinant human hyaluronidase PH20

Other medications used as support or escape medication for preventative, diagnostic, or therapeutic reasons, as components of the standard of care for a given diagnosis, may be considered as non-IPs.

7.1 Treatments Administered

The selection and timing of dose (Table 7.1-1) for each participant is as follows:

Table 7.1-1: Selection and Timing of Dose

Study Treatment	Unit Dose Strength(s)/Dosage Level(s)	Dosage Formulation Frequency of Administration	Route of Administration	Infusion Time
BMS-986258	8, 24, and 72 mg ^{a,b}	Q4W	IV	See note ^b
	200, 480, and 800 mg ^b	Q4W	IV	
	1200 mg ^b	Q4W	IV	
	1600 mg ^b	Q4W	IV	
	2400 mg ^b	Q4W	IV	
Nivolumab	480 mg ^b	Q4W	IV	30 minutes
BMS-986258 + ENHANZE® Drug Product (rHuPH20)	1200 mg	Once	SC	

Abbreviations: IV, intravenously; Q4, every 4 weeks; rHuPH20, recombinant human hyaluronidase PH20; SC, subcutaneous.

Protocol Amendment No.: 07

^a ENHANZE[®] (rHuPH20) is referred as rHuPH20 in the protocol

b For study drugs preparation and infusion times, please refer to the Pharmacy Manual.

Intravenous (IV) BMS-986258:

Participants in Part A, Part A1 (after the first dose), and NSCLC PD cohorts will receive IV BMS-986258 as monotherapy at doses ranging from 8 mg to 2400 mg. After the first dose, participants in cohort A1 will be offered the option to receive subsequent IV BMS-986258 in combination with nivolumab (480 mg) at the highest dose of BMS-986258 that has been shown to be safe and tolerable in the dose escalation (Part B). Treatment will be given Q4W twice per cycle, for up to twelve 8-week cycles (96 weeks).

There will be no dose escalations or reductions of BMS-986258 allowed. For Q4W dosing cycles, participants may be dosed within a ± 3 -day window.

BMS-986258 will be administered through an IV line. For details in study drug preparation and administration, refer to Pharmacy Manual.

Subcutaneous (SC) BMS-986258:

Participants in Part A1 will receive BMS-986258 plus rHuPH20 as an SC injection. BMS-986258 + rHuPH20 will be administered subcutaneously via a syringe pump (refer to Pharmacy Manual) on Cycle 1 Day1.

Nivolumab:

Participants in Part A1 who have received combination therapy and participants in Part B, Part B NSCLC PD, and Part C cohorts should receive nivolumab at a dose of 480 mg as a 30-minute infusion on Day 1 of each treatment cycle every 4 weeks until progression, unacceptable toxicity, withdrawal of consent, completion of of treatment, or the study ends, whichever occurs first. Participants should begin study treatment within 3 calendar days of treatment assignment.

There will be no dose escalations or reductions of nivolumab allowed. For Q4W dosing cycles, participants may be dosed within a ± 3 -day window. Premedications are not recommended for the first dose of nivolumab.

Participants should be carefully monitored for infusion reactions during nivolumab administration. If an acute infusion reaction is noted, participants should be managed according to Section 7.4.3.

Doses of nivolumab may be interrupted, delayed, or discontinued depending on how well the participant tolerates the treatment. Dosing visits are not skipped, only delayed. Nivolumab injection will be administered as an IV infusion over approximately 30 minutes.

